**10.3 Injury Management**

What was the intended injury management?	
 
● No intervention
 
● Non-operative
 
● Operative
 

Was there immobilisation during transfer?	
 
● Nothing
 
● Collar
 
● Trauma board
 
● Bed
 

Did the patient have surgical bedrest?	
 
● Nothing
 
● Bedrest, no logroll
 
● Bedrest + logroll
 
● Collar only
 

Traction?	
 
● Yes
 
● No
 

Did the patient receive any specialist therapy as an inpatient	
Yes No
 
If Yes, what type of therapy was provided?
 
 
- Speech and Language Therapy
 
- Tracheostomy care
 
- Physiotherapy
 
- Occupational therapy
 
- Alternative therapy – Ayurveda etc
 
- Other (specify _____)
 

Was spinal surgery performed?	
 
● Yes, performed at this institution
 
● Yes, transferred to a different institution for surgery
 
● No
 

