### **1.1 Primary Objective**

- Characterise case-mix, processes of care and variations in nonoperative and operative management strategies, including emergency, ward, surgical and ICU care, in patients presenting with traumatic spinal injury (TSI) between centres across low and high Human Development Index (HDI) countries

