### 3.5 Study measures

The following categories of routine clinical data will be collected prospectively for all patients included in the study. The full data set is included in *Appendix A*.

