### 4.2 Data Validation

A number of steps have been taken to ensure validation of all data entered.

- I. The dataset, web-based case report forms, and curation process has been designed according to DAQCOR principles.
- II. Web-based forms in the ORION platform contain fixed options at the point of data entry to maximise the likelihood of accurate and complete data capture at the point of collection.
- III. A local data validator independent to the local study team will be appointed at every participating institution. They will have access to a separate platform on Orion to ensure blinding to the rest of the data collected at their institution. They will be asked to complete a two-phase validation process, with a specific ORION validation user guide available to guide them through the process.
  - a. Prospective Case Acquisition: During the selected 4-week inclusion period, the local data validator will be asked to independently identify and collect all patient cases suitable for inclusion in the study. For validation, they will be required to prospectively collect these cases, recording the admission date, age at admission and AO injury type. This will subsequently be correlated with the data collected by their local team by the central study team.
  - b. Retrospective Operative Data: At 10 weeks from the start of the inclusion period (6-weeks following the end of the inclusion period), the local data validator will be asked to independently access operating theatre logs over the preceding 10 weeks. They will be required to document all the patients who have had an operation for TSI during this period and input the date and type of operation into the validation system where this corresponds to a patient admitted during the inclusion period. This will be used by the central study team to validate this specific cohort of their institution's cases.

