**10.2 Imaging Data**

Date/Time of first imaging	dd/mm/yyyy HH:MM
Most advanced type of imaging performed	
 
● Plain film radiograph
 
● Non-contrast CT Scan
 
● Contrast CT Scan
 
● MRI Scan
 

Anatomical area of spine included on imaging (Can select multiple)	
 
● Cervical
 
● Thoracic
 
● Lumbar
 
● Sacral
 

Level of fracture	
 
● Upper cervical
 
● Subaxial
 
● Thoracolumbar
 
● Sacral
 
● No injury
 

AO Classification of Injury	
Subluxation/Translation	
 
● Yes
 
● No
 

Traumatic herniated nucleus pulposis (not required if only plain radiograph available)	
 
● Yes
 
● No
 
 
If Yes:
 
 
● Please specify level:
 
● Cord compression: Yes/No
 

Haematoma (not required if only plain radiograph available)	
 
● Yes
 
● No
 

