**10.4 Operative Data (If “Yes, performed at this institution” to ‘Was spinal surgery performed?’)**

Grade of most senior surgeon present in the operating theatre	
 
● Fully qualified spinal surgeon
 
● Other qualified surgeon
 
● Surgical trainee
 
● Medical doctor
 

Type of anaesthesia	
 
● General
 
● Local
 
● None
 

Grade of most senior anaesthesia provider present in the operating theatre	
 
● Fully qualified anaesthetist with medical qualification
 
● Anaesthetist in training with medical qualification
 
● Not medically qualified anaesthesia provider
 
● Anaesthetic administered by the surgeon
 

Date of Operation	dd/mm/yyyy
Duration of operation	
 
● Less than 1 hour
 
● 1-5 hours
 
● 5-10 hours
 
● Over 10 hours
 

Were pre-incision prophylactic antibiotics given?	
 
● Yes
 
● No
 

Class of surgical wound	
 
● I Clean
 
● II Clean-contaminated
 
● III Contaminated
 
● IV Dirty-infected
 

Location of surgery	
 
● Cranio-cervical
 
● Cervical
 
● Thoracic
 
● Lumbar
 
● Sacral
 

What was the main procedure undertaken?
 
*If >1 procedure undertaken, refer to the main one
 
** Flow-Chart on ORION Platform **
	
 
● Open 
 
a. Approach: Anterior/Posterior/360
 
b. Minimally invasive surgery? Yes/No
 
c. Open Reduction? Yes/No
 
d. Direct decompression? Yes/No
 
e. In situ fusion? Yes/no
 
f. Fusion? Yes/No 
 
▪ Type of instrumentation 
 
● None
 
● OC
 
● C1/2
 
● Lateral mass
 
● Pedicle
 
● Anterior plating
 
● Bone graft
 
● Intervertebral fusion
 
● Lateral plating
 
 
 
 
 
○ Fluoroscopy used: Yes/No
 
 
 
● Closed 
 
○ Gardener Wells vs Halo
 
○ Mechanism of Maintenance: Collar vs Halo vs Bedrest
 
 
 

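### The Section 10.3 form fields are too coarse to describe variation in non-operative care, which is part of the primary objective

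*Combined protocol and SAP*

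**What the plan says.** Section 1.1 sets the primary objective: "Characterise case-mix, processes of care and variations in nonoperative and operative management strategies", across centres in low and high HDI countries. Section 3.5 points to the appendix for the patient-level fields ("The full data set is included in" Appendix A), and Section 4.2 says that the platform's web forms "contain fixed options at the point of data entry".

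Non-operative care is recorded mainly in Section 10.3:

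- Intended management: no intervention, non-operative or operative.
- "Was there immobilisation during transfer": nothing, collar, trauma board or bed.
- "Did the patient have surgical bedrest": nothing, bedrest without logroll, bedrest with logroll, or collar only.
- Traction: yes or no.
- Inpatient specialist therapy, with a list of types.
- Whether spinal surgery was performed: here, elsewhere after transfer, or not.

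Section 10.4 opens only when surgery was performed at the reporting institution. Its main-procedure item has a closed branch, which asks for Gardner-Wells or halo and then "Mechanism of Maintenance: Collar vs Halo vs Bedrest".

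**The concern.** A study of variation in non-operative care needs fields that can hold the common forms of that care, alone and in combination. The two immobilisation and bedrest fields in 10.3 are short fixed lists without a free-text alternative. Some treatments have no entry, and others depend on how a site reads the question.

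Two sites giving the same care could then produce different records. Section 5 plans to characterise processes of care from patient-level variables, to compare variance within and between sites, and to look for associations with HDI. Differences in coding would pass straight into those summaries. The validation in Section 4.2 would not catch most of them: the validator records admission date, age, AO injury type, and the date and type of operations, but not non-operative treatment.

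**Working it through.** The plan states no figure to reproduce. The check takes each form of care in turn and looks for a place to enter it in Appendix A.

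**Brace or orthosis.** No field in 10.1 to 10.5 lists one. The transfer and bedrest items have no *Other (specify)*, although transport, therapy, funding, intraoperative complications and discharge destination do. The general comment box is in 10.4 and so is closed to patients without surgery at the institution. The *Other* under specialist therapy asks about therapies, and nothing directs a site to enter a device there. This gap does not depend on whether fields accept one answer or several.

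**Halo.** It appears only in the closed branch of 10.4. Traction in 10.3 is yes or no and names no device. There are two possible paths:

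1. The site counts a closed halo procedure as spinal surgery. Section 10.4 opens, the halo is recorded, and the patient is classed as operated.
2. The site does not count it. Section 10.4 stays closed, the patient is classed as not operated, and the device is not recorded.

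The form does not say which reading is meant, so the split between operative and non-operative care can itself vary by site.

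**Collar plus bedrest.** The bedrest list has no combined option. If it accepts one answer, either the collar or the bedrest is lost. If it accepts several, ticking *Collar only* together with a bedrest option contradicts itself. The entry is defective either way.

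**Collar plus trauma board during transfer.** This depends on the selection mode, which is not stated. Five fields are explicitly marked as accepting several answers: other injuries (10.1), imaging area (10.2, "Anatomical area of spine included on imaging (Can select multiple"), funding and intraoperative complications (10.4), and adverse events (10.5). The transfer item is not marked. However, the specialist-therapy list in 10.3 and the instrumentation list in 10.4 are also unmarked, although several answers could apply. Single choice is therefore a reasonable inference and not an established fact.

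If the item is single choice, let a be the share with collar alone, b with board alone and c with both. True collar use is a + c. Recorded collar use lies between a (every patient with both entered as board) and a + c (every such patient entered as collar). The possible error is between 0 and c, and it depends only on site habit. For illustration, with assumed shares a = 10%, b = 10% and c = 60%, true use is 10% + 60% = 70% and recorded use can lie anywhere from 10% to 70%. These shares have no source in the documents, and the error disappears if the item accepts several answers.

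**The case against.** There is a fair case for the form as it stands. Section 3.3 says that the data set was refined with clinicians from low and high HDI settings, Section 4.1 plans a pilot of the platform, and Section 6 says that the study was not designed to investigate indications for, or efficacy of, specific management. Some coarseness is a deliberate choice. That supports a short form, but it does not meet an objective that names variation in non-operative strategy.

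Several stronger readings are tempting and should not be drawn:

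- *That the fields are exclusive and care will be misrecorded.* The documents never state the selection mode, and the live form is not shown. Care may be misrecorded or left unrecorded.
- *That braced patients are counted as untreated.* Intended management can still be entered as non-operative, and nothing is a true answer to a question about bedrest for a mobilised patient in a brace. What is lost is the device.
- *That a halo can never be recorded without open surgery.* Section 10.4 lists closed procedures and allows local or no anaesthesia, so the form may intend such cases to be entered there. The defect is that the form does not say so.
- *That false gaps in best practice will follow.* Section 5 identifies gaps chiefly by comparing provider-profiling summaries with best practice. Patient-level data also contribute to describing processes of care, so some effect is possible, but the documents do not trace one from these fields to a gap conclusion.

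Provider profiling (Section 3.2) might describe available devices, but each institution completes it once, so it cannot restore what an individual patient received.

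**Conclusion.** The point holds in a limited form. Three parts follow from Appendix A as written: no field offers a brace or orthosis; a halo patient's classification depends on an undefined reading of spinal surgery; and collar plus bedrest has no coherent entry. A fourth part, the loss of collar plus board during transfer, is conditional on the item being single choice.

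Between-site and HDI comparisons of non-operative care may therefore partly reflect coding habit, and orthotic treatment goes unrecorded as such. The size cannot be estimated, because the documents give no frequencies for these devices or combinations. The conclusion assumes that the platform follows Appendix A, as Section 3.5 implies. It concerns data capture only and takes no view on treatment.

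**What to change.** In Appendix A and on the platform:

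1. Make transfer immobilisation a select-all-that-apply item.
2. Split the bedrest item in two: (a) bedrest: none, without logroll, with logroll; (b) external immobilisation, select all that apply: none, collar, halo, brace or orthosis, other (specify). Open (b) to every patient, whatever the answer on surgery.
3. State on the form whether a closed halo or traction procedure counts as spinal surgery, so that all sites classify it alike.

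The cost is one extra tick list per patient and a small change to the form. No new procedure is needed, because the information should be in routine notes. The change is best made before sites start: detail missed at entry could be recovered only by going back to local notes at each site.

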#### Initial injury and admission data

- Baseline demographics e.g. age, gender
- Type and mechanism of injury
- Pre-hospital timeline, transfers and transportation
- Clinical presentation on arrival to hospital e.g. GCS, Kampala Trauma Score, Frankel grade
- Initial injury details
- Admission details

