#### Injury management data

- Intended injury management
- Injury management during transfer e.g. immobilisation
- Specialised therapies received e.g. physiotherapy, speech and language therapy

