Road Traffic Collision (RTC) 
 
● RTC Pedestrian
 
● RTC Cyclist
 
● RTC Motorcyclist
 
● RTC Motorcyclist (passenger)
 
● RTC Car (driver)
 
● RTC Car (passenger)
 
● RTC other vehicle (driver)
 
● RTC other vehicle (passenger)
 
 Fall 
 
● Fall standing height
 
● Fall from height
 
	Assault 
 
● Assault – no weapon
 
● Assault – blunt instrument
 
● Assault – sharp instrument
 
● Assault – firearm
 
 Other 
 
● Self-harm
 
● Other violence
 
● Animal attack
 
● Explosion
 
● Industrial accident (outside categories listed above)
 
● Sport/recreational activity
 
		
Date/Time of admission to hospital	dd/mm/yyyy HH:MM		
Was the patient directly transferred from the site of the accident to the current institution?	
 
● Yes
 
● No
 
		
Mode of transport to primary institution	
 
● Air ambulance (helicopter)
 
● Land ambulance (paramedic staffed)
 
● Land ambulance (not paramedic staffed)
 
● Public Transport
 
● Police
 
● Private vehicle
 
● By foot
 
● Other (specify _____)
 
		
Method of transport to the current institution	
 
● Air ambulance (helicopter)
 
● Land ambulance (paramedic staffed)
 
● Land ambulance (not paramedic staffed)
 
● Police
 
● Private vehicle
 
● By foot
 
● Other (specify _____)
 
		
GCS on arrival to your institution (if intubated on arrival, please state pre-intubation GCS)	
 
● Eye Response 
 
○ Open spontaneously - 4
 
○ Open to verbal command - 3
 
○ Open to pain - 2
 
○ No eye opening - 1
 
 
 
● Verbal Response 
 
○ Oriented - 5
 
○ Confused - 4
 
○ Inappropriate words - 3
 
○ Incomprehensible sounds - 2
 
○ No verbal response - 1
 
○ Intubated - T
 
 
 
		

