### 10.5 Outcome Data

Death within the 6-week follow-up period?	
 
• Yes
 
• No
 
 
If Yes:
 
 
• Date of death: dd/mm/yyyy
 
• In ICU at time of death? Yes/No
 

Discharged within the 6-week follow-up period?	
 
• Yes
 
• No
 
 
If Yes:
 
 
• Date of discharge: dd/mm/yyyy
 
• Destination of discharge: 
 
○ Transfer to another hospital
 
○ Transfer to a rehabilitation unit
 
○ Usual place of residence/Home
 
○ Absconded
 
○ Other (specify _____)
 
 
 

Was the patient admitted to intensive care at any point during the 6-week follow up period?	
 
• Yes
 
• No
 
 
If Yes:
 
 
• Date of admission to ICU: dd/mm/yyyy
 
• Was the patient discharged from ICU during the 6-week follow up period? Yes/No
 
 
If Yes:
 
 
• Date of discharge from ICU: dd/mm/yyyy
 

Was the patient intubated during admission?	
 
• Yes
 
• No
 

Did the patient require a tracheostomy?	
 
• Yes
 
• No
 

Was the patient requiring ventilatory support at time of death/the end of the 6-week follow up period (whichever event occurs first)?	
 
• Yes
 
• No
 

Did any adverse events of special interest occur in the 6-week follow-up period? (Select all that apply)	
 
• None
 
• Pressure Ulcer
 
• Pneumonia
 
• Pulmonary embolism
 
• Deep venous thrombosis
 
• Decubitus Ulcer
 

	
 
• Urinary tract infection
 
• Symptomatic haematoma
 
			
Did any surgical site infections occur in the 6-week follow-up period?	
 
• Yes
 
• No
 
 
If Yes:
 
 
• Required antibiotics only
 
• Required debridement
 
• Required removal of metalwork
 
			

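### The single immobilisation item does not name the journey it covers and has no not-applicable or unknown answer, so comparisons by site and HDI may partly reflect interpretation and arrival mix

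*Combined protocol and SAP*

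**What the plan says.** The item in Appendix A, 10.3 reads "Was there immobilisation during transfer". Its answer list is "Nothing ● Collar ● Trauma board ● Bed". No origin, destination or leg is given. There is no answer for a patient to whom the question does not apply or whose journey is not known. Section 3.5 (Injury management data) is the only other description, "Injury management during transfer e.g. immobilisation", and it adds no definition.

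Elsewhere the form separates the legs of the journey. Appendix A, 10.1 has a Yes/No item, "Was the patient directly transferred from the site of the accident to the current institution", then one field headed "Mode of transport to primary institution" and another for transport to the current institution.

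The word transfer is used in several ways:

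- In the 10.1 Yes/No item it covers the journey from the scene.
- In 10.3, the same table as the immobilisation item, an answer to the surgery question is "Yes, transferred to a different institution for surgery".
- In 10.5 a discharge destination is "Transfer to another hospital".
- Section 3.5 lists "Pre-hospital timeline, transfers and transportation", naming transfers and transportation separately.

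Section 5 makes patient-level process variables part of the primary descriptive analysis, with stratification by site, country and HDI.

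**The concern.** One code, *Nothing*, can carry two meanings: the patient was moved without protection, or the question did not apply because there was no inter-hospital move. For a referred patient, a recorded collar could belong to the scene leg, the inter-hospital leg or both.

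The study sets out to describe variation in care and to find where good practice is lacking. The Background names inadequate pre-hospital care as a challenge in lower-income settings and expects substantial variation in that phase. This item is one of the few patient-level fields on how patients were handled before arrival.

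Any misreading is likely to cluster by site. The registration form (Appendix B) allows a lead and up to two further team members, so one interpretation can govern a site's whole cohort and then look like a real difference in practice. The validation in 4.2 would not reveal it: the validator records admission date, age, AO injury type, and operation date and type, but not immobilisation.

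**Working it through.** The plan gives no figure for this item, so there is nothing to reproduce. The check has two parts.

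**1. Which reading does the text settle?**

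| Place | Meaning of transfer | Effect if applied to the item |
|---|---|---|
| 10.1, Yes/No item | Scene to current institution | Applies to direct arrivals; *Nothing* means moved without immobilisation |
| 10.3, surgery item | Outward move to another institution | Inter-hospital sense; direct arrivals fall outside it |
| 10.5, discharge destination | Move to another hospital | Inter-hospital sense |
| 3.5, admission data | Listed apart from transportation | Suggests a narrower sense than any journey |

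No sentence links any of these usages to the immobilisation item, so the text does not settle it.

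**2. How much could it matter for direct arrivals?**

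Inputs, all assumed and none in the documents:

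- p = true share immobilised, taken as 60% for both direct and referred patients
- d = share of patients arriving directly
- m = share of direct arrivals entered as *Nothing* because the item was read as inter-hospital, taken as unrelated to whether they were immobilised

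All other answers are taken as correct. The recorded share is then p × (1 − d × m).

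| d | m = 0 | m = 25% | m = 50% | m = 100% |
|---|---|---|---|---|
| 30% | 60% | 55.5% | 51% | 42% |
| 50% | 60% | 52.5% | 45% | 30% |
| 70% | 60% | 49.5% | 39% | 18% |

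Worked case: 0.60 × (1 − 0.30 × 0.50) = 0.51, and 0.60 × (1 − 0.70 × 0.50) = 0.39. Two groups with the same true practice and the same rate of misreading would differ by 51 − 39 = 12 percentage points through arrival mix alone.

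Extreme case: if every direct arrival at a site is so entered (m = 100%) and direct arrivals are 40% to 80% of its patients, the recorded share is 0.60 × 0.60 = 36% down to 0.60 × 0.20 = 12%. A site reading the item as any journey would record 60%.

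**Referred patients.** Let s be the share immobilised on the scene leg and h the share on the inter-hospital leg. A site reading the item as the scene leg records s, and one reading it as the inter-hospital leg records h. A site counting either leg records at least the larger of the two. The documents give neither s nor h, so I put no number on this part.

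**The case against.** The strongest reply is that the form's own question on arrival route calls the direct journey from the scene a transfer. A site that carries this over to 10.3 answers properly for direct arrivals, and that part of the problem disappears. This stands as a plausible reading, but the same table and 10.5 use the word for inter-hospital moves, and the leg stays unclear for referred patients.

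Second, Appendix A is only a field list. It refers to a flow chart on ORION for the main procedure (10.4), so some logic sits outside the document, and the item may be clearer on screen. Section 4.1 also plans a pilot of the platform that could expose unclear wording. This stands too. Still, applicability notes are printed for other items, such as those in 10.2, and not for this one.

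Third, the Yes/No field lets analysts report the item by arrival route, and an implausible excess of *Nothing* among direct arrivals at a site would show up. That helps in part, but it cannot recover what each *Nothing* meant.

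Fourth, the item is not an outcome and no named model uses it. That is correct and limits the weight of the point.

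A reader might infer more than the documents support:

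- **That a direct arrival can only be entered as *Nothing*.** Section 4.2 says the forms have fixed options. It does not say the field is mandatory, so a blank is not ruled out.
- **That this is the only pre-hospital treatment recorded.** The GCS item in 10.1 also picks up intubation before arrival, and provider profiling (3.2) covers pre-hospital frameworks and resources.

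**Conclusion.** The point holds as a data-definition weakness in one descriptive process variable. The journey is not named, there is no not-applicable or unknown answer, and the documents' varied use of the word leaves more than one reasonable reading. Once data are entered, the ambiguity cannot be fully undone.

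Its size is unknown. On the assumed inputs, the moderate case is a spurious 12-point gap (51% against 39%). It rests on 60% true immobilisation, half of direct arrivals misentered, and direct-arrival shares of 30% and 70%. The 36% to 12% range might be taken as the expected effect, but it is an all-or-nothing extreme in which every direct arrival at a site is entered as *Nothing*. At the other end, with m = 0, direct arrivals carry no bias. The referred-patient problem remains on any of these assumptions.

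Nothing here touches mortality, Frankel grade or the other outcomes. The documents do not show that immobilisation has been misrecorded, only that the form as printed allows it.

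**What to change.** Ask the item once per leg, matching the transport fields: immobilisation *on the journey from the scene*, and immobilisation *on the journey from another hospital*. Open the second only when the direct-arrival question is answered No. Add *unknown* to both, because a receiving hospital may not know how a referred patient was moved from the scene. State whether more than one answer may be selected. Use the scene item as the pre-hospital measure and report results by arrival route. The pilot in 4.1 is a natural place to test the wording.

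The cost is one added conditional item on ORION and some unknown answers for the scene leg of referred patients.

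If ORION already carries help text that defines the journey, put that definition in Appendix A. If data have already been collected, state which journey was intended, report the item separately for direct and referred patients, and note that *Nothing* may include patients to whom the question was thought not to apply.
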